#### **9.2.8 Period 2 Telephone Contact (Phone 4, Day 35)**

Each patient will be contacted by phone by the study coordinator, to inquire about the occurrence of AEs, concomitant medications, compliance to study treatment and use of the BM/BSFS diary.

#### **9.2.9 End-of-Study (Day 43, Visit 5)**

At Day 43, the final clinic visit, all patients will return to the clinic with their BM and BSFS diaries, and the remaining study medication. Patients will arrive in the fasted state (i.e. fast for 4 hours before visit). The following assessments and procedures will be performed:

1. Complete physical examination;
2. Measurement of vital signs including heart rate, blood pressure and body temperature;
3. Measurement of body weight, and calculation of BMI;
4. A 12-lead ECG;
5. All safety laboratory tests, including at a minimum: urinalysis (dipstick), hematology, serum chemistry;
6. A urine pregnancy test will be performed if applicable;
7. Recording of concomitant medications;

8. Study drug compliance check - patients will return all study medication from Period 2 to the study coordinator. Drug accountability will be performed.
9. Verification of completion of the BM and BSFS diaries for Washout and for Period 2. The diaries will be given back to the study coordinator.
10. The VAS symptoms questionnaire will be completed by the patient on site.
11. Recording of AEs.

AEs still ongoing at the time of the visit will be assessed and evaluated for further follow-up as necessary. SAEs occurring during the 30-day period following the End-of-Study, Day 43 visit, should be reported to the medical monitor. (See Serious Adverse Event Reporting section for details)

## **10. INVESTIGATIONAL PRODUCT MANAGEMENT**

### **10.1 Packaging, Labeling, and Shipping**

The Sponsor will be responsible for ensuring the Test and Placebo investigational products are manufactured in accordance with Good Manufacturing Practice (GMP); the labeling should also comply with applicable regulatory requirement(s).

Study medication will be provided in patient kits containing enough medication for one period (14 days). Each patient kit consists of 2 labeled bottles packed inside a labeled carton. Patients randomized to “high” dose will receive 2 bottles of ECC, and patients randomized to “low” dose will receive 1 bottle of ECC and 1 bottle of matching placebo. Study medication will be specifically identified and will bear instructions to ensure proper order of intake at all times. Each bottle and carton label will bear a unique number linked to a randomized medication list to identify the kit contents (i.e. high dose or low dose treatment). Both bottles contained within one kit will have the same number as the outer carton. The randomized medication list will be linked to the patient randomization schedule at the IWRS level.

Each bottle and patient kit box will bear a label that conforms to the appropriate local regulations.

Shipments of patient kits to the clinical sites will be done using a Sponsor-defined courier. A temperature data logger will accompany the shipment to ensure an adequate chain of custody. Excursions outside of 15°C to 30°C will be promptly reported to the Sponsor.

### **10.2 Storage, Dispensing and Compliance Verification of Study Drug**

All patient kits will be shipped from the Sponsor or Sponsor resources to the clinical sites. Patient kits will be provided to study subjects only.

Upon receipt of the patient kit shipper container, the pharmacy site staff should record the receipt, date, time, and temperature of the product based on inspection or on the temperature logger reading. Any study drug that arrives in improper storage conditions or is damaged in any way must be reported to the Sponsor as soon as possible and shall not be administered until instructed otherwise. Each clinical site will maintain an inventory record of the patient kits received, stored (in a secure restricted area), and dispensed.

At the clinical sites, patient kits are to be stored under labeled storage conditions in a secure location with limited access. Any temperature excursions outside of 15°C to 30°C will be promptly reported to the Sponsor.

Upon instructions from the IWRS, the pharmacy site staff will, at the time of dispensing, formally identify and remove the assigned Patient Kit box(es) from storage and will cross-check the expiry date on the labels on the Patient Kit box(es) with the target dates of use, at a minimum. The necessary Patient Kits will be sent to the site staff actually dispensing the study drug to the patients.

### **10.3 Study Drug Accountability**

At Visit 2, the patient will receive one Patient Kit box which will contain sufficient study drug for Period 1. At Visit 3, the patient will return to the site the Patient Kit box containing all the remaining study drug from Period 1. The next dispensing visit is Visit 4 where the patient will receive another Patient Kit box which will contain sufficient study drug for Period 2. At the End-of-Study visit, the patient will return to the site the Patient Kit box containing all the remaining study drug from Period 2. If a patient withdraws or discontinues from the trial, they will be requested to return all study supplies promptly.

Complete and accurate records regarding the receipt, dispensing, and return or destruction of study drug for each patient in the study will be kept. Any used study drug containers, as well as any unused containers or unused portions of containers, or patient kits must be maintained until accounted for by the study monitor. Drug accountability will be performed at the end of each period to confirm that the required amount of study drug has been consumed. If the amount of study drug is not as expected, the patient will be contacted for clarification. After drug accountability by the monitor and approval from the Sponsor, the study drug and containers should be destroyed per the CRO's procedures.

## **11. TREATMENT AND PROTOCOL COMPLIANCE**

Patients are expected to self-administer oral daily doses based on the protocol schedule and have all procedures done within the allowable time windows (detailed in the Schedule of Activities).

Regardless of allowable visit windows, each period or study drug treatment cycle should always be 14 calendar days. Investigational drug will then be supplied for this 14 consecutive days period. A 14-day treatment-free period (Washout) will be included between the 2 dosing periods.

In the event a patient misses a scheduled assessment visit, this should be rescheduled for the earliest possible date, no more than 2 days later. Patients who are persistently noncompliant may be withdrawn from the study at the investigator's or the Sponsor's discretion.

The following measures will be employed to ensure treatment and protocol compliance:

- Patients will be given clear instructions prior to study drug dispensing on how to self-administer the study drugs.
- Patients will be given clear instructions and reminders during each visit and telephone contact on how to use the BSFS and BM diary.
- Patients will be contacted by telephone on Days -8, 7, 21 and 35 to confirm continued compliance with the dosing regimen, use of concomitant medication, and use of BM/BSFS diaries.
- BM/BSFS diaries will be checked for compliance at each visit.

### 11.1 Permitted and Prohibited Concomitant Medications

The standard of care for patients with SBS includes several medications, nutritional recommendations and procedures destined to improve their quality of life, treat symptoms and prevent complications. This section outlines the general study-specific requirements in terms of concomitant medications, vitamin supplements and potential drug interactions.

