	
12. Subjects who took an Investigational Product (IP) in the 30 days prior to the first study drug administration
 
13. Any other clinically significant condition that is considered by the principal investigator as being susceptible to put the patient at greater safety risk, influence response to study product, or interfere with study assessments.

Number of Sites and Patients	3 clinical sites and 18 patients
Treatments	
Product: ECC capsules, 425 mg (size 00)
 
In order to fully blind the study, the double dummy technique will be used, i.e. the lowest dose (1.7 g daily) will be co-administered with an ECC matching placebo.
 
Treatment A (“low” dose): 1.7 g total daily dose of ECC, BID + placebo
 
Treatment B (“high” dose): 4.25 g total daily dose of ECC, BID
 
Mode of administration: Oral, capsules taken at least 30 minutes before breakfast and the evening meal
 
Manufacturer: Pharmascience Inc.

Concomitant Medications	
Concomitant antidiarrheal drugs, such as loperamide, are allowed as long as their dose and dosing regimen remain stable at least 2 weeks before and for the total duration of the study.
 
Antacid medications, such as H2 antagonists, and OTC products are prohibited. PPIs are allowed as long as their dose and dosing regimen are stable during the study. IBS-D medications, spasmolytics and any drug exerting significant effects of gastrointestinal transit are also prohibited. Gut trophic factors such as growth hormone and GLP-2 are also prohibited.
 
Standard of Care, concomitant medications are allowed during the study only if judged essential by investigator and with a stable dose and dosing regimen for at least 2 months prior to enrolment and during the study. However, loperamide dose may be modified by the investigator if absolutely necessary. Loperamide doses will be recorded in the patient diary, on a daily basis.

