As an anion exchanging resin, cholestyramine may also bind other drugs that are administered concurrently. Cholestyramine resin may delay or reduce the absorption of concomitant oral medications such as thyroid and thyroxine preparations, warfarin, hydrochlorothiazide (acidic), phenylbutazone, phenobarbital, tetracycline, penicillin G, and digitalis, as well as therapeutic bile acids such as ursodiol and obeticholic acid. These medications are mostly absorbed in the proximal portion of the small intestine, such as the duodenum and the proximal jejunum. This is where a complexation with cholestyramine may occur. Thus, patients are recommended to take other drugs either one hour before, or 4-6 hours after, taking cholestyramine which is an inconvenience for most patients (13, 19, 20).

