### **Drug-Drug Interaction Study with New ECC Formulation**

A second Phase I, single-dose, cross-over, drug-drug interaction (DDI) study was conducted to investigate the effect of ECC on plasma kinetics of hydrochlorothiazide (HCTZ), used as a victim drug, in healthy volunteers. Cholestyramine powder is known to substantially reduce bioavailability of HCTZ as measured by plasma levels and urinary excretion of HCTZ. The effects of this DDI have been shown to be time-dependent and heightened by multiple dosing. Results of the study showed that both formulations of cholestyramine (ECC capsule and powder) exhibit an effect on the fasting pharmacokinetics of HCTZ. However, the impact of ECC is notably lower than the impact of the cholestyramine powder on HCTZ and is therefore expected to be of minor clinical significance compared to that of the non-enteric-coated powder formulation. The results suggest that the delivery of cholestyramine in a more distal intestinal segment via an enteric-coated capsule, successfully reduces the magnitude of DDIs. Overall, ECC was generally safe and well-tolerated by the subjects in this study.

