### 11.2 Permitted Medications

All standard of care drugs will be permitted, unless they are listed in the Prohibited Medications List section. However, dose and dosing regimen of permitted drugs must remain constant during the whole study duration, until Day 42.

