### 11.3 Prohibited Medications

After consulting the protocol, in case of doubt about a patient's concomitant medication, study personnel should consult with the Sponsor before enrolling/pursuing participation of a patient on study. If a medication other than those specified in the protocol (including OTC) is used after the first treatment administration or at any time before the end of the study, the Sponsor will decide whether the subject will be permitted to remain in the study, depending on the drug used, the time of drug intake, etc. The drug and dose taken will be noted.

Prohibited medications include:

- H2 receptors antagonists: cimetidine, famotidine, ranitidine and nizatidine (should be stopped at least 72 hours prior to Day 0 visit)
- Pancrelipase supplements
- Prostaglandin E drugs, such as misoprostol (should be stopped at least 24 hours prior to Day 0 visit)
- Over the counter antacid medications, containing: bismuth salts, aluminium and magnesium hydroxide, sodium alginate, sodium bicarbonate, etc. (should be stopped at least 24 hours prior to Day 0 visit)
- Drugs used to treat Diarrhea Predominant Irritable Bowel Syndrome (IBS-D), such as: alosetron (*Lotronex*), eluxadoline (*Viberzi*), rifaximin (*Xifaxan*), lubiprostone (*Amitiza*), linaclotide (*Linzess*) and trimebutine (*Modulon*) (should be stopped at least 72 hours prior to Day 0 visit)
- Antispasmodic drugs, such as dicyclomine (should be stopped at least 24 hours prior to Day 0 visit)
- Prokinetic drugs, such as: domperidone and metoclopramide (should be stopped at least 48 hours prior to Day 0 visit)
- Any kind of pre-, and probiotics (should be stopped at least 72 hours prior to Day 0 visit)
- Bile acids sequestrants, such as regular cholestyramine, colestipol and colesevelam (should be stopped at least 72 hours prior to Day 0 visit)
- Any kind of orally administered antibiotics, unless judged absolutely necessary by the investigators (should be stopped at least 72 hours prior to Day 0 visit)
- Gut trophic factors such as growth hormone and GLP-2 are also prohibited (should be stopped at least 48 hours prior to Day 0 visit)
- Products containing cannabinoids.

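### Section 11 sets no spacing between ECC and interacting oral drugs, and the plan fixes the dose of those drugs to Day 42 with an exception for loperamide only

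*Combined protocol and SAP*

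**What the plan says.** - **Section 11.1** states the scope: "This section outlines the general study-specific requirements in terms of concomitant medications, vitamin supplements and potential drug interactions".
- **Section 11.2** permits standard-of-care drugs that are not on the prohibited list, and adds that "dose and dosing regimen of permitted drugs must remain constant during the whole study duration, until Day 42".
- **Section 11.3** lists the prohibited drugs and sends doubtful medications to the Sponsor. The only entry that clearly meets the interaction list in 5.4 is "Any kind of orally administered antibiotics, unless judged absolutely necessary by the investigators".
- **The synopsis (Concomitant Medications)** allows standard-of-care drugs only if the investigator judges them essential, and "with a stable dose and dosing regimen for at least 2 months prior to enrolment and during the study". It states one exception: "However, loperamide dose may be modified by the investigator if absolutely necessary".
- **Section 5.4** gives examples of oral drugs whose absorption cholestyramine may delay or reduce. It reports that "patients are recommended to take other drugs either one hour before, or 4-6 hours after, taking cholestyramine". This is background on conventional cholestyramine.
- **Section 5.5 (drug-drug interaction study)** says of powder and hydrochlorothiazide (HCTZ): "The effects of this DDI have been shown to be time-dependent and heightened by multiple dosing". It reports that "both formulations of cholestyramine (ECC capsule and powder) exhibit an effect on the fasting pharmacokinetics of HCTZ", that the effect of ECC was notably smaller, and that it should matter little clinically compared with powder.
- **Section 7.3** ties ECC to breakfast and the evening meal, at least 30 minutes before each, and to no other drug. Table 2 contains no INR.

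**The concern.** The protocol names the hazard in its background and announces rules for it in 11.1, but the operative sections contain none. As written, nothing in 11.2, 11.3 or the dosing instructions keeps warfarin, thyroxine or digitalis from being swallowed together with ECC. The stability rule adds to this. Such a drug is held at one dose while the resin starts, stops and starts again, and the plan provides for a change of dose only with loperamide. Patient care and consistent handling at the 3 sites are at stake. The efficacy result is not.

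**Working it through.** The plan states no figure on this point, so the check is a comparison of sections with some short counts.

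**1. Announced against delivered.** Section 11.1 names three topics. Concomitant medications are covered by 11.2 and 11.3. Drug interactions get no spacing, monitoring or dose-adjustment rule in either. Vitamin supplements are not mentioned in either.

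**2. How much of the 5.4 list stays permitted.** Section 5.4 names warfarin, thyroid preparations, digitalis, HCTZ, phenobarbital, phenylbutazone, ursodiol, obeticholic acid, tetracycline and penicillin G: 10 entries. The oral-antibiotic entry in 11.3 restricts the last two, so 10 - 2 = 8 remain. The bile-acid entry in 11.3 covers sequestrants, not therapeutic bile acids. Other defensible counts are:
- thyroid and thyroxine split: 11 - 2 = 9 of 11;
- the two therapeutic bile acids taken as one class: 9 - 2 = 7 of 9;
- obeticholic acid read as barred by the synopsis clause on drugs affecting transit: 10 - 3 = 7 of 10.

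Every count gives most of the list. The list itself consists of examples, so no fraction is exact.

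**3. Exposure compared with the evidence.** ECC doses: 2 per day x 14 days = 28 per period, and 28 x 2 periods = 56. The ECC interaction evidence is one victim drug in a single-dose study in healthy volunteers. Resin exposure changes 4 times: on at Day 1, off after Day 14, on at Day 29, off after Day 42. The first 3 changes fall inside the freeze in 11.2. The fourth comes as the freeze ends.

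**4. What the existing routes do.**
- The synopsis test of essential need and exclusion 13 (8.2) control who enters. They set no timing for patients who do.
- Sponsor consultation (11.3) operates where staff have a doubt, one patient at a time.
- Sections 13.1 and 13.6 provide monitoring and care once an adverse event has occurred.
- Section 18.1 allows an urgent departure, documented as a deviation.

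None sets spacing in advance, and none makes a needed dose change part of the plan.

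**5. How many patients.** The documents do not say. If a share p of patients takes such a drug, the chance of at least one among 18 is 1 - (1 - p)^18. Assuming p = 0.01 gives 0.166, and assuming p = 0.20 gives 0.982. A range of 17% to 98% settles nothing.

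**6. Whether spacing is workable.** Keeping a drug at least 1 h before or 4 h after ECC blocks 1 + 4 = 5 h per dose. Two doses block at most 10 h and leave at least 24 - 10 = 14 h. With 6 h after, 2 x (1 + 6) = 14 h are blocked and 10 h remain.

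**7. Effect on the analysis.** The ITT population (14.2) does not depend on concomitant regimens. The per-protocol definition names prohibited medications, not changes of regimen.

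**The case against.** The strongest case against the point has four parts.

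- **The background concerns powder.** Section 5.4 says the listed drugs are absorbed mostly in the proximal small bowel, while ECC is designed to release further down. This stands in part. Powder spacing is not automatically right for ECC, and the documents do not show an ECC interaction with warfarin, thyroxine or digitalis. But ECC did affect HCTZ, and the expectation of minor clinical significance rests on that one drug and is relative to powder.
- **The plan already has controls.** It does, and a reader might infer from Section 11 alone that patients are unprotected. The documents do not support that, because the routes in step 4 of the working are real. What remains is that they act case by case or after the event.
- **Spacing may not breach 11.2.** A reader might infer that moving a drug by some hours is already a deviation. The protocol does not define regimen to include clock time, so this is one interpretation only. The restriction on dose is clear, and the synopsis exempts only loperamide.
- **Other instructions may exist.** Section 10.1 says the study medication will bear instructions on intake, and Section 11 promises patients clear directions. The Brochure, consent form and label text were not available, so spacing advice may exist there. It would not alter the dose freeze in the protocol.

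On vitamins, a reader might infer from the synopsis wording on OTC products that supplements are banned. In 11.3 the OTC entry on the prohibited list is confined to antacids, so this needs clarification only.

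**Conclusion.** The point holds as a gap in conduct and patient care. Section 11 announces interaction requirements and gives no spacing from ECC, and a foreseeable, clinically needed dose change of a permitted drug such as warfarin is a protocol deviation. Most of the drugs that 5.4 gives as examples are covered by this. The 8 of 10 count should not be read as a measured share, because the list is open-ended and the count depends on convention.

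The size in patients is unknown, and so is the size of any ECC interaction with drugs other than HCTZ. Nor should a reader infer a threat to the efficacy result: the ITT analysis does not change, and regimen changes are not named in the per-protocol definition. Confidence is moderate, because it rests on the protocol text without the Brochure, consent form or labels. The change is worth making because the hazard is one that the protocol itself describes.

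**What to change.** Add a short paragraph to 11.2, with a matching line in the synopsis:

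1. As a precaution, interacting oral drugs such as those in 5.4 are taken at least 1 h before or at least 4 h after each ECC dose, or at another interval that the sponsor justifies for ECC. Any retiming is done before the Day -14 diary starts, so that baseline and treatment weeks are recorded under the same schedule. It does not count as a regimen change under 11.2 or the 2-month rule in the synopsis.
2. Clinically required dose changes of narrow-margin drugs such as warfarin are allowed and recorded, as for loperamide. Usual-care monitoring continues when ECC starts and stops. After Day 42 no exception is needed, because the freeze has ended. The exception need not extend to obeticholic acid, since 7.1.2 describes bile acid modulating agents of that kind as able to reduce bowel movement frequency.

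As a clarification, one clause can say whether non-prescription vitamins are permitted.

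The cost is a protocol amendment, minor inconvenience for patients on these drugs, and a slightly looser stability rule. The loosening concerns drugs not expected to drive bowel frequency, which is a clinical judgement for the sponsor to confirm. No visit, study test or diary field is added, and the primary endpoint and its analysis stay as they are.

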### 11.2 Permitted Medications

All standard of care drugs will be permitted, unless they are listed in the Prohibited Medications List section. However, dose and dosing regimen of permitted drugs must remain constant during the whole study duration, until Day 42.

### 11.3 Prohibited Medications

After consulting the protocol, in case of doubt about a patient's concomitant medication, study personnel should consult with the Sponsor before enrolling/pursuing participation of a patient on study. If a medication other than those specified in the protocol (including OTC) is used after the first treatment administration or at any time before the end of the study, the Sponsor will decide whether the subject will be permitted to remain in the study, depending on the drug used, the time of drug intake, etc. The drug and dose taken will be noted.

Prohibited medications include:

- H2 receptors antagonists: cimetidine, famotidine, ranitidine and nizatidine (should be stopped at least 72 hours prior to Day 0 visit)
- Pancrelipase supplements
- Prostaglandin E drugs, such as misoprostol (should be stopped at least 24 hours prior to Day 0 visit)
- Over the counter antacid medications, containing: bismuth salts, aluminium and magnesium hydroxide, sodium alginate, sodium bicarbonate, etc. (should be stopped at least 24 hours prior to Day 0 visit)
- Drugs used to treat Diarrhea Predominant Irritable Bowel Syndrome (IBS-D), such as: alosetron (*Lotronex*), eluxadoline (*Viberzi*), rifaximin (*Xifaxan*), lubiprostone (*Amitiza*), linaclotide (*Linzess*) and trimebutine (*Modulon*) (should be stopped at least 72 hours prior to Day 0 visit)
- Antispasmodic drugs, such as dicyclomine (should be stopped at least 24 hours prior to Day 0 visit)
- Prokinetic drugs, such as: domperidone and metoclopramide (should be stopped at least 48 hours prior to Day 0 visit)
- Any kind of pre-, and probiotics (should be stopped at least 72 hours prior to Day 0 visit)
- Bile acids sequestrants, such as regular cholestyramine, colestipol and colesevelam (should be stopped at least 72 hours prior to Day 0 visit)
- Any kind of orally administered antibiotics, unless judged absolutely necessary by the investigators (should be stopped at least 72 hours prior to Day 0 visit)
- Gut trophic factors such as growth hormone and GLP-2 are also prohibited (should be stopped at least 48 hours prior to Day 0 visit)
- Products containing cannabinoids.

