#### 9.2.1 Screening and Eligibility Assessments (Visit 1, Day -15)

On Day -15 prior to randomization, interested SBS patients will undergo a screening session, Visit 1. Patients will arrive in the fasted state (i.e. fast for 4 hours before visit). This visit is comprised of the following elements:

1. Verification of identity and demographics (age, gender, race);
2. Confirmation of the SBS diagnosis will be obtained, with proper medical history data;
3. Description of the type and extent of intestinal surgical resection will be provided (if applicable);
4. Verification of all inclusion and exclusion criteria;
5. Collection of medical history including history of intestinal surgical resection or other possible cause of SBS, all current medications and therapies, non-prescription drug intake, and HPN if still administered. Particular attention will be paid to obtaining the history of diarrhea in the 3 months prior to screening, as well as prohibited drugs;
6. Measurement of body weight and height, and calculation of BMI;
7. Measurement of vital signs including heart rate, blood pressure and body temperature;
8. Complete physical examination;
9. An ECG will be performed;
10. All safety laboratory tests including hematology, serum chemistry, pregnancy test (if applicable) and urinalysis (dipstick). Screening laboratory results must be available and reviewed by the Investigator before randomization.
11. Patients will be given a bowel movement (BM) and BSFS diary, in which they will need to record daily the number of stools and their form, using the BSFS. Proper instructions will be provided for the use of the BSFS. Patients will be instructed to start recording in this Screening diary at Day -14 and to fill it out daily until Day -1 inclusive, in order to establish a baseline and confirm patients' eligibility.
12. All screening results must be available prior to Day 0 randomization so that the study Investigator can determine eligibility.
13. From screening to the first dose of the study, AEs will be recorded as screening events or as part of the medical history, as applicable.

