#### 9.2.2 Screening Telephone Contact (Phone 1, Day -8)

Each patient will be contacted by phone by the study coordinator, to inquire about the occurrence of AEs, any changes in medications, and use of the BM and BSFS screening diary.

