## 12. EFFICACY ASSESSMENTS

### 12.1 Weekly Number of Bowel Movements

The total number of bowel movements (defecations) occurring during the second week of ECC treatment (Days 8 to 14) compared those occurring during screening in the week prior to randomization, will be used to assess the primary endpoint. Use of loperamide will also be recorded. Bowel movements will be recorded by the patients on a daily basis, as follows:

- each day of the last 14 days of the screening period, prior to randomization, to establish the first baseline and confirm subject eligibility
- each day of the first 14-day treatment period
- each day of the 14-day washout period
- each day of the second 14-day treatment period

[figure not shown]
In summary, this implies that occurrences of bowel movements will be recorded daily by the patient, in the diary, from Day -14 (screening) up to Day 42, i.e. the last dosing day of the study.

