## **14. STATISTICAL ANALYSIS**

A statistical analysis plan (SAP) will provide details of the methods of analysis to address all study objectives. The SAP may be amended during the course of the study but will be finalized before the database hard-lock for any analysis.

Data summaries by treatment group will be presented. For continuous variables, data will be summarized with the number of patients, mean, standard deviation, median, and minimum and maximum values by treatment group. For categorical variables, data will be tabulated in frequency tables to display the number and proportion of patients for each category by treatment group. Baseline assessments for each outcome variable will be defined as the last measurement obtained before the first dose of study drug.

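### Stop times for prohibited bowel-active drugs run back from Day 0, so up to 4–6 of the 7 primary baseline days may be on drug, biasing the uncontrolled tests of each dose

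*Combined protocol and SAP*

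**What the plan says.** Section 11.3 lists prohibited drugs and ties each stated stop time to the Day 0 visit:

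- 72 hours for sequestrants ("Bile acids sequestrants, such as regular cholestyramine, colestipol and colesevelam (should be stopped at least 72 hours prior to Day 0 visit"), H2 antagonists, IBS-D drugs, pre- and probiotics, and oral antibiotics.
- 48 hours for gut trophic factors and prokinetics ("Prokinetic drugs, such as: domperidone and metoclopramide (should be stopped at least 48 hours prior to Day 0 visit").
- 24 hours for antispasmodics, prostaglandin E drugs and over-the-counter antacids.

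Section 12.1 sets the primary comparison. Week 2 counts are "compared those occurring during screening in the week prior to randomization, will be used to assess the primary endpoint". The same screening diary serves "to establish the first baseline and confirm subject eligibility". Section 14 gives the general rule: "Baseline assessments for each outcome variable will be defined as the last measurement obtained before the first dose of study drug".

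Three other places touch on these drugs:

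- The Synopsis says "any drug exerting significant effects of gastrointestinal transit are also prohibited".
- At Visit 1, "Particular attention will be paid to obtaining the history of diarrhea in the 3 months prior to screening, as well as prohibited drugs".
- The Day -8 call is made "to inquire about the occurrence of AEs, any changes in medications, and use of the BM and BSFS screening diary".

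None of them sets an earlier stop date. The stability rules (two weeks for loperamide, two months for standard-of-care drugs) cover permitted drugs only.

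Section 14.6.1 tests the high dose (step a), then the low dose (step b), as a within-patient change from baseline against zero. Only then does it compare the doses (step c). Section 7.2.1 has every patient on active ECC in both periods.

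**The concern.** Baseline and Week 2 can be measured under different background medication. The drug is allowed for most of the baseline week and prohibited during treatment, so its withdrawal enters the change from baseline. Steps a and b have no control to absorb it.

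The bias can go either way:

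- **Sequestrant before Day 0.** It lowers the baseline count, so ECC's effect is understated. This direction is conservative.
- **Drug that speeds transit, such as a prokinetic.** It raises the baseline count, so stopping it can pass for an ECC benefit. Section 7.1.2 itself links higher frequency to faster transit.

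Inclusion criterion 10 is judged on the same diary. It tends to remove sequestrant users whose diarrhea is well controlled. It does not remove users of a drug that raises frequency.

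At stake is the proof-of-concept claim for each dose, and access to step c, which is reached only through steps a and b.

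**Working it through.** **Inputs from the plan.** Baseline Days -7 to -1 (Section 12.1). Stop times of 72, 48 and 24 h before Day 0 (Section 11.3). SD of change 2.0, planned change 4 per week, correlation 0.80, alpha 0.05, n=18 (Section 14.1).

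**Plan's own figures.** SD of the between-dose difference = √(2 × 2.0² × (1 − 0.80)) = 1.265. A paired t-test at two-sided 0.05 and 80% power reproduces all 16 rows of Table 3, including 15 patients for a difference of 1.0. The planned 18 equals 15 × 1.2. Power for a change of 4 with SD 2 and n=18 exceeds 99.9%, which agrees with the stated figure of more than 80%.

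**Baseline days still open to the drug (whole days).**

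| Rule | Baseline days allowed | Count of 7 | Count of 14 diary days |
|---|---|---|---|
| 72 h | -7 to -4 | 4 | 11 |
| 48 h | -7 to -3 | 5 | 12 |
| 24 h | -7 to -2 | 6 | 13 |

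Counting the part-day before the cut-off would add one day to each. Earlier stopping is also compliant, so these are maxima.

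**False benefit (assumed prokinetic effect of +2 to +4 per week on 5 of 7 days, no ECC effect).** Excess baseline per user = 2 × 5/7 = 1.43 to 4 × 5/7 = 2.86 movements per week. The mean excess is that times the share of users. False improvement comes from simulation: 400,000 trials per setting, one-sample t-test on the change, two-sided 0.05, favourable direction counted, SD 2, n=18. The intended rate is 2.5%.

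| Users | Mean excess per week | False improvement, step a |
|---|---|---|
| 0% | 0 | 2.5% |
| 2% | 0.03–0.06 | 2.8–3.2% |
| 5% | 0.07–0.14 | 3.4–4.3% |
| 10% | 0.14–0.29 | 4.6–7.1% |
| 25% | 0.36–0.71 | 10.0–21.8% |
| exactly 1 of 18 | 0.08–0.16 | 3.4–4.0% |
| exactly 2 of 18 | 0.16–0.32 | 4.5–6.5% |
| exactly 4 of 18 | 0.32–0.63 | 7.9–15.5% |

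At n=15 the rates are slightly lower: 4.3–6.3% at 10% users and 8.8–18.2% at 25%. A separate simulation with stronger assumptions (0.5 to 1 movement per day on 4 to 6 days) gave 5.5% with 2 users of 18 at the mild end. It gave 22–30% with 4 users at 1 per day.

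**Conservative direction (assumed sequestrant effect of 2 to 4 per week on 4 of 7 days).** Loss per user = 2 × 4/7 = 1.14 to 4 × 4/7 = 2.29. The mean change is understated by 0.02–0.05 (2% users), 0.11–0.23 (10%) or 0.34–0.69 (30%). Against the planned 4 this runs from 0.02/4, about 1%, to 0.69/4 = 17%. With 30% users losing 2.29 each, step a power is 0.999 at n=15 and 1.000 at n=18. The upper value of 4 is borrowed from the ECC planning value in Section 14.1; it is not a figure for conventional resin.

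**Step c.** With one screening baseline B for both doses, (B − high) − (B − low) = low − high, so B cancels and only the gating is affected.

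**If Period 2 had its own baseline.** Section 12.1's reference to a first baseline leaves this open. Only Period 1 data, 9 of 18 patients per dose, could then be affected. Step a rates become 2.7–2.8% (2% users), 2.9–3.3% (5%), 3.4–4.3% (10%) and 5.2–8.6% (25%).

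**The case against.** The timing mismatch is plain, but its consequence can fairly be disputed.

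- **The sequestrant case does little harm.** It is conservative and leaves power intact under the plan's assumptions. The harmful case rests on other drugs.
- **Prokinetic use and effect are assumed.** The documents do not say that patients with three months of stable chronic diarrhea use prokinetics, or that these drugs add 2–4 movements a week.
- **Other rules reduce the number affected.** Exclusion 4 bars diarrhea from causes other than SBS. Criterion 10 asks for stability over the 14-day diary. Section 11.3 tells staff to consult the sponsor when in doubt.
- **The missing placebo is the larger weakness.** An assumed common shift of 0.5 movements a week alone gives 17% false improvement at n=18; one prokinetic user moves that to 20–23%.
- **The remedy has limits.** The Day -8 call has a one-day window and may fall inside the baseline week. For 72 h drugs it can only detect a late stop. The Schedule of Activities (footnote 8) limits prior medications to those ongoing at Day -15, so a drug begun during screening might be missed.
- **A separate SAP could already handle this.** Section 14 defers details to one, and its text is not available here.

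Most of this stands as a limit on size. It does not close the gap. None of the safeguards sets a stop date, and criterion 10 has no numerical stability rule. Footnote 8 still captures the main case, a drug already in use at Visit 1. The lack of placebo is the reason to protect the baseline, since nothing else supports steps a and b.

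**Conclusion.** The concern holds. On the plan's own wording, a compliant patient may take a prohibited bowel-active drug on up to 4, 5 or 6 of the 7 primary baseline days, and steps a and b then read its withdrawal as part of the treatment effect. The overlap is permitted, not certain, and the bias is possible, not shown.

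The false-benefit risk is small if 2–5% of patients are affected. It reaches roughly two to three times the intended 2.5% at 10%, or with 2 users of 18. The 25% row is an upper bound, not an expectation. The sequestrant direction costs at most 17% of the planned change under the stated range and does not threaten planned power. All sizes rest on assumed user shares and drug effects, with SD 2. They would be about halved in mean bias if each period had its own baseline.

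It is worth fixing because the remedy is cheap and a few patients matter among 18. Confidence in the wording gap is high; confidence in a material effect is moderate at best.

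**What to change.** In Section 11.3, keep the intervals but count them back from Day -7. Drugs then stop by about Day -10 (72 h), Day -9 (48 h) or Day -8 (24 h), and no baseline day is open to them. Give the instruction at Visit 1 (Day -15), where prohibited drugs are already asked about, and check it at the existing Day -8 call. No visit moves.

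For patients already enrolled, use the medication record to flag any Section 11.3 drug taken on Days -14 to -1. Report steps a and b with and without those patients as a sensitivity analysis, written into the SAP before database lock. With one or two such patients it will carry limited information, but it shows whether the result depends on them.

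The cost is a wording change and a small analysis. Because it alters conduct, it would probably be a substantial amendment under Section 18.2. Affected patients go about 7 days longer without the drug. The eligibility diary could still hold 4, 5 or 6 on-drug days of 14, against 11, 12 or 13 now. Counting from Day -14 would clear that too, but it requires stopping before Visit 1.
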